The use of sputum for molecular genetic analyses is limited by its cellular heterogeneity which includes 1% of bronchial epithelial cells and greater than 95% macrophages and neutrophils (74). Enrichment of bronchial epithelial cells has been achieved by magnetic cell sorting (MACS) or fluorescent cell sorting techniques. We will perform positive selection of epithelial cells and inflammatory cells using magnetic bead preparations or fluorescent cell sorting techniques. Human epithelial cells will be purified from sputum according to the expression of CD326 (human epithelial antigen, HEA, or epithelial cell adhesion molecule (EpCAM) using the magnetic bead CD326 (EpCAM) Tumor Cell Enrichment and Detection Kit (Miltenyi Biotech). To confirm purity of our isolation for selected samples, epithelial cell identification will be demonstrated by intracellular pan-cytokeratin staining. Cells will immediately be placed in RNAsprotect Cell Reagent (QIAGEN) and RNA isolated and fractionated into low molecular weight (LMW) and high molecular weight (HMW) using the miRNeasy mini kit (QIAGEN). RNA will be quantified and quality assessed. We will collaborate with the NYU Cancer Institute (CI) Genomics Services. We will have access to high-throughput genomic and computational methodologies specifically for microRNA. We will use the GeneChip® miRNA Array. Briefly, LMW RNA will be labeled with a FlashTag labeling kit (Genisphere, Inc.) according to the manufacturer's protocol. Samples will be incorporated into a hybridization mix and applied to an affymetrix chip and scanned. Computational analysis with techniques such as principal component analysis will be performed with analytic services provided through the NYU CI Genomics core facility. Data will be log transformed and only miRNA replicates that are detected at levels of 2 standard deviations above the average background will be considered for further analysis. These studies will provide us with distinct miRNAs that may differ between IA, AA and controls, or IA and AA. If specific miRNAs are identified that are different between IA, AA and controls, or IA and AA, we will further validate expression of the miRNA using quantitative real time PCR.

SA2.b. We will identify the mRNA targets of the differentially expressed miRNAs by using publicly available databases and correlate miRNA and mRNA expression.

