Most miRNA bind to target-3'UTR and function as translational repressors most often by promoting the degradation of mRNA. Each miRNA may regulate up to 200 target genes (42). We therefore propose to correlate patterns of miRNA changes in our defined populations, with mRNA expression arrays. HMW RNA from isolated epithelial cells will be used for hybridization to Affymetrix HG-U133 Plus 2.0 microarrays. Images will be analyzed in the core facility and data will be normalized as follows: (1) per array, by dividing the raw data by the 50th percentile of all measurements; and (2) per gene, by dividing the raw data by the median expression level for all the genes across all arrays in a data set. We will determine whether up or down-regulated mRNAs are potential targets for previously identified miRNAs.

Specific Aim 3: To test the hypothesis that levels of RNA of targets in human sputum cells will differ before and after the administration of inhaled corticosteroids in asthmatics (both IA, AA). The rationale for this aim of the study is to

investigate which markers are steroid sensitive and which are steroid resistant which would provide information for therapeutic targeting in asthma.

SA3.a. We will isolate RNA targets in discrete sputum cells from induced sputum in IA and AA individuals and compare levels before and after administration of inhaled corticosteroids.

In this second phase of the study, (Phase II) we will enroll AA or IA individuals who have fit enrollment criteria for the phase I part of the study and participated in phase I of the study and were able to provide us with an acceptable sputum sample. These participants will be recontacted for participation in Phase II if they signed permission to be re-contacted. We will obtain a repeat sputum sample as baseline for the Phase II study. An inhaled corticosteroid (Fluticasone HFA 220 mcg, 1 puff twice daily) and large volume spacer will be provided. Inhalation technique and a daily diary will be reviewed. Subjects will be instructed to use Fluticasone propionate 220 mcg q puff twice daily and to record their use in a written diary. A repeat sputum sample will be obtained after 2 weeks of Fluticasone propionate use.

Sputum samples will be processed for discrete cells and RNA levels (mRNA, miRNA) will be analyzed to understand the effect of ICS use on RNA expression in discrete sputum cell populations.

Statistical Analysis:

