We were able to develop basic techniques and measurement from 10 patients in each group as initially proposed in the previous version of this protocol. We now propose to increase our enrollment from 30 to 50 subjects in each group based on the recruitment and enrollment data of about 30% of screen failures (33 subjects screen failed out of 108 total). In addition, there have been subjects who have not been able to produce sputum or provide adequate number of sputum cells for analysis (38 subjects out of 65 accrued gave adequate sputum samples). This represents about 60% success rate for sample quality. Therefore, we will need to increase our enrollment numbers to achieve an n=30 per group.

Power Analysis: Based on a similar rate of screen failures and inadequate samples, the analysis is now based on 50 patients in each group. Our group sample sizes of 50 and 50 achieve 90% power to detect a difference of 0.73 given the null hypothesis that the two-group difference is 0 and the estimated group standard deviations are 1.0 and 1.0, with a significance level (alpha) of 0.05 using a two-sided two sample t-test. We will work with [name], our biostatistician for our statistical analysis.

For ENO and EBC analyses, we will express data as means \pm SD for normally distributed variables. For variables that are not normally distributed we will use medians and the interquartile range. We will use statistical analysis including unpaired *t* tests, Kruskal-Wallis test, and regression coefficients as appropriate. P values of < 0.05 will be considered significant. Differential expression of miRNA and hierarchical clustering will be performed with the genomics core. Statistics using *t* tests or algorithms designed specifically for data mining and biochip interpretation will be used. Pathway analyses will also be performed by the genomics computational core.

Anticipated results and alternative approaches

We will continue to recruit patients with WTC exposure or with asthma based on our experience in our asthma registry or our WTC clinic, in which most people are willing and anxious to participate in any study that might help characterize their symptoms.

We plan to also submit an advertisement to the IRB for approval and to use research match (researchmatch.org) a national registry which is a secure, web-based approach as a recruitment method, and will post the advertisement.

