We have chosen to use individuals with WTC dust cloud exposure as our model of initial high dose exposure to enhance our ability to identify patients with irritant asthma. We suspect that other more prolonged exposures also induce irritant asthma, but our previous studies and those of other investigators suggest that this exposure provides the highest risk.

We have proposed a positive selection strategy for isolation of bronchial epithelial cells from IS. The possibility exists that this technique may provide too low a yield of cells. Should that be the case, we can use a negative selection strategy using anti-CD14 and anti-CD16 antibody beads to specifically deplete macrophages and neutrophils respectively (37). We may also need to obtain duplicate sputum samples from patients, i.e. have patients return for a second sputum induction.

Our initial analyses will be between our healthy controls and asthma in general (AI and AA) and subsequently between each type of asthma (AI and AA) to optimize our ability to detect differences in sputum markers and miRNA. The

possibility exists that we will find no difference between measurements of markers of inflammation in exhaled breath between AI and AA. Should that be the case, we will have to examine whether our pilot study was powered to identify a small difference.

We are basing our miRNA and mRNA studies on those that have been performed in epithelial cells derived from cigarette smokers (45). These studies have shown a correlation between mRNA and miRNA expression and thus there is precedent for our studies. Because of the high price of each of these chips, and the cost of core analysis time, we initially propose to use 5 subjects for each condition to obtain a global pattern scale. These studies will subsequently be extended to get a reasonable statistical power.

From our pilot studies and recent publication we will continue to investigate mechanisms of asthma and irritant-induced asthma. The studies are high risk but have potential for high yield, and will provide data for subsequent NIH applications for replication and further evaluation for a junior faculty member. In addition, they have potential to provide information that could help target specific interventions for asthma of different phenotypes as we proposed in phase II of the study. As such, they fit the mandate of the CTSI grants.

II. Characteristics of the Research Population

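### No false-discovery control is named for the miRNA comparisons and no calling rule for the mRNA arrays, so the list behind Aim 2 could carry an unknown and possibly large false share

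*Combined protocol and SAP*

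**What the plan says.** The Statistical Analysis section under Research Design and Methods gives the array work to a core facility: "Differential expression of miRNA and hierarchical clustering will be performed with the genomics core". It then permits t tests or an unnamed alternative: "algorithms designed specifically for data mining and biochip interpretation will be used". The sentence just before these two is "P values of < 0.05 will be considered significant". Apart from the alpha levels in the sample-size statements, that is the only significance rule in the plan, and its paragraph opens with exhaled nitric oxide (ENO) and exhaled breath condensate (EBC). Section III.2 (Data Analysis and Data Monitoring) repeats this text. No false-discovery, family-wise, permutation or fold-change rule appears anywhere.

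Other relevant text:

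- **SA2.a** applies a detection filter at 2 SD above background. For miRNAs found to differ it says "we will further validate expression of the miRNA using quantitative real time PCR". It does not say in whose samples.
- **SA2.b** describes how mRNA arrays are normalised and matched to predicted miRNA targets. It gives no test or threshold for calling an mRNA up- or down-regulated.
- **Anticipated results and alternative approaches** sets two contrasts: controls against all asthma, then irritant (IA) against allergic (AA) asthma. On array numbers it says "we initially propose to use 5 subjects for each condition", with a later extension of unstated size.

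**The concern.** A miRNA array yields hundreds of simultaneous tests. At P < 0.05 without adjustment, a list of apparently different miRNAs is almost certain even if none differs. Divergent miRNA regulation is the central hypothesis in the Specific Aims and the whole of Aim 2, so that hypothesis could look supported by chance alone.

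The steps around the test do not settle this. The detection filter reduces how many miRNAs are tested but does not control error among those left. qPCR on the arrayed samples would confirm the measured levels, but a chance imbalance between the sampled groups would be reproduced along with them.

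**Working it through.** **Inputs from the documents.** Threshold 0.05; 5 per condition at the start; 30 analysable and 50 enrolled per group; standardised differences of 0.73 SD (Statistical Analysis) and 1.3 SD (section III.2).

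**Assumptions, because the documents give no figure.** The number of miRNAs tested, m, is 300 to 1000. The share that truly differ, π, is 5% to 30%. Differences of 1 SD and 2 SD are added to those in the plan.

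**1. The plan's own figure.** There is no false-discovery figure to reproduce. The nearest is the power statement: "Our group sample sizes of 50 and 50 achieve 90% power to detect a difference of 0.73", with SD 1.0 and "with a significance level (alpha) of 0.05 using a two-sided two sample t-test". The exact t calculation gives 95.1%, not 90%. That is a separate matter and hardly affects this point, since both values enter the same formula in step 3.

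**2. No miRNA differs.** Expected false calls per contrast = 0.05 × m:

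- m = 300: 0.05 × 300 = 15
- m = 1000: 0.05 × 1000 = 50

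This needs no assumption about π or effect size.

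**3. Some miRNAs differ.** False share of calls = 0.05(1 − π) / [0.05(1 − π) + power × π]. For 5 per group, 2 SD and π = 5%: 0.0475 / (0.0475 + 0.791 × 0.05) = 0.0475 / 0.0870 = 55%. The value of m cancels.

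| Per group, difference | Power | π = 5% | 10% | 20% | 30% | Half or more false only if π is at most |
|---|---|---|---|---|---|---|
| 5, 0.73 SD | 17.5% | 84% | 72% | 53% | 40% | 22% |
| 5, 1.3 SD | 44% | 68% | 51% | 31% | 21% | 10% |
| 5, 2 SD | 79% | 55% | 36% | 20% | 13% | 5.9% |
| 30, 0.73 SD | 79% | 55% | 36% | 20% | 13% | 5.9% |
| 30, 1 SD | 97% | 50% | 32% | 17% | 11% | 4.9% |
| 50, 0.73 SD | 95% | 50% | 32% | 17% | 11% | 5.0% |

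The last column is 0.05 / (0.05 + power). With the plan's stated 90% power the row would read 51%, 33%, 18%, 12%.

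The table assumes equal groups, as in IA against AA. For controls against all asthma at the start (5 against 10), power at 0.73 SD is 23.4%. At π = 5% the share is then 0.0475 / (0.0475 + 0.234 × 0.05) = 80%.

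**4. Effect of Benjamini-Hochberg at 5%.** Simulated ordinary t tests on independent miRNAs, m = 1000, of which 50 truly differ:

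| Per group, difference | P < 0.05: false, true | Benjamini-Hochberg: false, true |
|---|---|---|
| 30, 1 SD | about 48, 48 | about 2, 36 to 37 |
| 5, 2 SD | about 48, 39 | about 0.2, 2 |

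The mean false share per experiment is about 5% in both cases. A moderated t statistic was not simulated.

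**The case against.** The strongest reply is that the plan does not commit to the practice criticised. The 0.05 rule sits in a paragraph about ENO and EBC, and the core may use array software that already controls false discovery. This stands in part: a reader might infer that P < 0.05 will be applied to every feature on both arrays, and the documents do not say so. No mRNA t test is stated at all. But plain t tests are expressly permitted for miRNA, no other threshold is offered, and nothing requires the unnamed algorithms to control false discovery.

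A second reply is that this is pilot work meant to give preliminary data, with 5 arrays per condition as a first look. That is fair, and treating those arrays as a ranking step is close to the plan's own intent. It does not remove the need for a rule, because Aim 2 is framed as a hypothesis test and the results are meant to support grant applications and help target interventions.

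A third reply is that qPCR and target matching protect against false calls. A reader might infer that qPCR uses the same RNA as the arrays. The documents do not say this, so the gap is that the samples are unspecified. Target matching may help, especially as SA2.b also plans to correlate miRNA with mRNA. But the plan notes that "Each miRNA may regulate up to 200 target genes". If 5% of mRNAs were called by chance (an assumption, as no mRNA rule is given), a miRNA with the full 200 targets would gain 200 × 0.05 = 10 matches by chance.

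**Conclusion.** The point stands as an omission that should be corrected: no false-discovery control is named for the miRNA comparisons, and no calling rule for mRNA. The firmest result is the one for no true difference: about 5% of tested miRNAs called per contrast if plain t tests at P < 0.05 are used.

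A reader might infer that half or more of the called miRNAs will be false. The documents do not support that as a general statement. The false share depends on how many miRNAs truly differ and by how much, and neither figure is given. For 5% to 30% truly different, it runs from about 11% to 55% with 30 to 50 per group (0.73 to 1 SD) and from about 13% to 84% with 5 per group (0.73 to 2 SD). With 30 to 50 per group it reaches half only if about 5% to 6% or fewer differ. At 5 per group and 0.73 SD it does so for anything up to 22%.

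It would also go too far to require qPCR in participants kept off the arrays. With 30 analysable per group and 5 arrayed, that would mean about 25 per group. It would compete with the planned extension of the arrays and use scarce material: 38 of 65 accrued subjects gave adequate sputum, and epithelial cells are about 1% of sputum cells.

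**What to change.** In the Statistical Analysis section and section III.2:

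- State that, for each contrast (all asthma against control; IA against AA), a miRNA or mRNA is called differentially expressed only at a Benjamini-Hochberg false-discovery rate of 5% or less, preferably with a moderated t statistic. Report the number of features tested.
- Use the initial 5-per-condition arrays to rank candidates only, not as evidence for the Aim 2 hypothesis.
- State that qPCR on arrayed samples confirms the assay and not the group difference.

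The change needs wording and routine core-facility output, and no new participants. The price is fewer calls. With 1000 miRNAs tested and 50 truly different, about 36 to 37 of the 50 would be found at 30 per group and 1 SD, against about 48 without adjustment. At 5 per group and 2 SD, about 2 of the 50 would be found, against about 39. That low yield is why the first arrays suit ranking and not testing.

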H#: 10-01191
NCT02740543

Title: Biomarkers of Irritant-Induced and Allergic Asthma – Phase I and Phase II

Principal Investigator: [name]
 Co-Investigator: [name]
 Professional Study Personnel: [name]
 [name]
 [name], MA
 [name]

Specific Aims

Asthma is a heterogeneous disease, and although much is understood about mechanisms of inflammation in allergic asthma, less is known about mechanisms of irritant-induced asthma (IA) (5, 7). Understanding the underlying similarities and differences in mechanisms of these two types of asthma will help focus current treatments and lead to development of new therapies. We have a longstanding NYU/Bellevue Asthma registry (NYUBAR), with a large population (N = 900) of asthma cases and controls, a program that has been housed at the CTSI (formerly GCRC). The destruction of the World Trade Center (WTC) resulted in massive dust, gas and fume exposures to local residents, workers and cleanup workers and individuals involved in rescue and recovery and adverse respiratory health effects of this disaster are reported more than 7 years after 9/11 (1-4). Many responders, as well as those exposed as residents or local workers, have developed IA, asthma that arises after a lag from an environmental exposure (1, 5, 6). The WTC Environmental Health Center (WTC EHC) is one of the three New York City (NYC) WTC Centers of Excellence and the only one that focuses on treatment and monitoring of local workers and residents. As such, it has a large population of individuals with irritant-induced asthma. We now propose to use participants from the NYUBAR and the WTC EHC to expand our knowledge of irritant and allergic asthma. Non-invasive studies allow for the assessment of airway inflammation, a non-specific response to environmental exposure and injury. Recent technologies also allow for assessment of microRNA (miRNA), small RNAs that regulate gene expression at the post-transcriptional level and thus serve as a pathway to regulation of inflammation. **We will test the hypothesis that airway inflammation in irritant and allergic asthma may be similar, but result from divergent miRNA regulatory pathways expressed in sputum cells.** These studies will provide preliminary data for future studies that will help identify biological pathways to categorize these asthma phenotypes and target future treatment interventions. We propose the following aims:

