Specific Aim 1: To test the hypothesis that irritant-induced asthma is characterized by elevated markers of inflammation in a manner similar to that described for allergic asthma.

SA1.a We will identify and phenotype individuals with WTC dust cloud-exposed irritant-induced asthma (IA), individuals with allergic asthma (AA) and healthy unexposed individuals (Controls).

SA1.b We will measure biomarkers of inflammation using noninvasive techniques for exhaled nitric oxide (ENO) and 8-isoprostanate from exhaled breath condensate (EBC) in WTC irritant-induced asthma (IA), individuals with allergic asthma (AA) and in healthy unexposed individuals (Controls).

SA1.c We will measure inflammatory cells in induced sputum from individuals with IA, AA and Controls.

Specific Aim 2: To test the hypothesis that the miRNA expression in airway epithelial cells will differ between IA, AA and Control individuals.

SA2.a. We will isolate RNA from epithelial cells and inflammatory cells in induced sputum and assess the miRNA expression profile using microarray technology among individuals with irritant-induced asthma (IA), individuals with allergic asthma (AA) and healthy unexposed individuals (Controls).

SA2.b. We will identify the mRNA targets of the differentially expressed miRNAs by using publicly available databases and correlate miRNA and mRNA expression.

Specific Aim 3: To test the hypothesis that levels of RNA of targets in human sputum cells will differ before and after the administration of inhaled corticosteroids in asthmatics (both IA, AA). The importance of this hypothesis in the characterization of irritant induced and allergic asthma is to further characterize the regulatory pathways expressed in sputum cells by identifying which inflammatory markers are steroid sensitive and steroid resistant.

SA3.a. We will isolate RNA targets in discrete sputum cells from induced sputum in IA and AA individuals and compare levels before and after administration of inhaled corticosteroids.

I. Background and Significance

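### The IA–AA similarity part of the hypothesis is paired only with tests of difference, and a null result on exhaled-breath markers leads to a power look-back that cannot show which differences the data exclude

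*Combined protocol and SAP*

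**What the plan says.** The overall hypothesis in Specific Aims is that "airway inflammation in irritant and allergic asthma may be similar", with the divergence expected in miRNA pathways. Specific Aim 1 is the hypothesis that "irritant-induced asthma is characterized by elevated markers of inflammation in a manner similar to that described for allergic asthma". AA patients are enrolled and measured alongside IA patients and controls, so a concurrent IA–AA comparison is available.

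All the planned inference concerns difference. Under Statistical Analysis, the power statement is that "group sample sizes of 50 and 50 achieve 90% power to detect a difference of 0.73". Its null value is zero, so it describes a test of difference. The listed methods are unpaired t tests, Kruskal-Wallis and regression coefficients, with the rule "P values of < 0.05 will be considered significant". The analysis text under Data Analysis and Data Monitoring (section III.2) repeats these methods and this rule.

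Anticipated results and alternative approaches orders the comparisons as controls against all asthma, then IA against AA, with the aim of detecting differences. It foresees that exhaled-breath markers may not differ between IA and AA. Its only response is that "we will have to examine whether our pilot study was powered to identify a small difference". The documents give no number for a small difference, no equivalence margin and no confidence-interval rule. No corresponding step is given for sputum cell counts.

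**The concern.** For inflammation markers, little or no IA–AA difference is what the similarity hypothesis predicts, yet the plan treats it as a contingency. A non-significant test does not establish similarity, because the same result often occurs when the groups truly differ by a moderate amount. The planned look at power describes what the design could have detected. It does not say which differences the observed data rule out, which is what a reader needs in order to judge similarity. The data are meant to feed later grant applications, so a null IA–AA finding would be carried forward without a stated way to interpret it.

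**Working it through.** **Inputs.** From Statistical Analysis: SD 1.0 in each group, two-sided alpha 0.05, two-sample t-test, 50 per group in the power statement, and a target of 30 per group with usable sputum. The 30 agrees with the stated yield: 38/65 = 58.5%, and 50 × 38/65 = 29.2. ENO and EBC do not themselves need an adequate sputum sample, so both 30 and 50 are shown. True differences of 0.3 and 0.5 SD are assumptions for illustration; the documents put no figure on a small difference.

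**The plan's own figure.** With n = 50 per group and a difference of 0.73, the noncentrality is 0.73/√(2/50) = 3.65 on 98 degrees of freedom. Power is 95.1%, not the stated 90%. The difference detectable with 90% power at n = 50 is 0.65 SD; 0.73 SD needs about 41 per group. At n = 30, power for 0.73 SD is 79.4%. The mismatch is on the safe side at 50 per group, and the present point does not depend on it.

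**How often a real difference gives P > 0.05.** Power comes from the noncentral t distribution with df = 2n − 2 and noncentrality d/√(2/n). The chance of non-significance is 1 − power.

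| True IA–AA difference | n per group | Noncentrality | Power | Non-significant |
|---|---|---|---|---|
| 0.5 SD | 30 | 1.94 | 47.8% | 52% |
| 0.5 SD | 50 | 2.50 | 69.7% | 30% |
| 0.3 SD | 30 | 1.16 | 20.8% | 79% |
| 0.3 SD | 50 | 1.50 | 31.8% | 68% |

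The power column also shows that the look-back for any fixed small difference can be answered before data are collected. If small means 0.3 SD, the answer is 21% at 30 per group and 32% at 50.

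**What a confidence interval would give.** The 95% half-width is t(0.975, 2n − 2) × √(2/n), taking the sample SD at its assumed value of 1.0.

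- n = 30: 2.002 × 0.2582 = 0.52 SD
- n = 50: 1.984 × 0.2000 = 0.40 SD

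An observed difference near zero would therefore exclude differences beyond about 0.52 SD or 0.40 SD respectively. That can be stated without any margin.

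**Could 0.73 SD serve as a similarity margin?** Suppose similarity is declared when the 95% interval lies wholly inside ±0.73 SD. The probabilities below integrate over the sampling distribution of the SD.

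| True difference | n = 30 | n = 50 |
|---|---|---|
| 0 | 59% | 90% |
| 0.5 SD | 14% | 21% |

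Such a rule counts a 0.5 SD difference as similar by definition, and would declare similarity in 14% to 21% of studies where that difference is real.

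**The case against.** **Aim 1 can be read as a question about elevation.** The background notes that it is unknown whether ENO is also raised in IA. On that reading the question is whether markers are raised in IA as already described for AA, and difference tests against controls can answer it. This stands, and it limits the point to IA–AA similarity. It does not remove the point, because Specific Aims states IA–AA similarity directly and AA is measured concurrently. A reader might infer that the plan cannot answer Aim 1 at all; the documents do not support that.

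**Power for a fixed difference is not observed power.** A reader might infer that the look-back only restates the P value. That criticism applies to power computed at the observed effect. The sentence, read plainly, asks about a fixed small difference, and that power depends on sample size and SD rather than on the P value. The accurate criticism is narrower: no size is given, and the answer does not show what the data exclude.

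**The plan never says a null will be taken as similarity.** This also stands. By asking whether the study was too small, the plan leaves room for an inconclusive reading. The weakness is that no method of interpretation is given.

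**Scope and purpose.** The look-back covers exhaled-breath markers only. For sputum, the plan also has eosinophil and neutrophil cut-offs that allow a descriptive comparison. The study calls itself a pilot giving preliminary data, so a formal equivalence test is not obligatory. That argues for estimation with intervals, which is the change proposed here.

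**Conclusion.** The point holds for the IA–AA similarity part of the hypothesis. That part is matched only with tests of difference, and the one response to a null exhaled-breath result is a check of power for an unquantified difference. Given a true 0.5 SD difference, non-significance would occur 52% of the time at 30 per group and 30% at 50, so a null P value is weak evidence of similarity. These figures assume normal data with common SD 1.0, as in the plan's power statement, equal groups, and 0.5 SD as an illustrative moderate difference. Skewed markers would need the same reasoning on the log scale.

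A reader might also take ±0.73 SD as a ready-made equivalence margin. The documents do not support that: it is a generic detectable difference, tied to no named marker and not justified as a difference small enough to ignore. In a pilot the matter should be corrected, but it does not undermine the study.

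**What to change.** In Anticipated results and alternative approaches, replace the sentence on examining power with text to this effect:

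- For each Aim 1 marker (ENO, EBC 8-isoprostane and pH, sputum cell counts), report the IA minus AA difference with its 95% confidence interval, as a ratio from the log scale where the data are skewed.
- A non-significant P value will not be taken as evidence of similarity. Conclusions will rest on which differences the interval excludes, and inconclusive is an allowed result.
- 0.73 SD may be shown as a reference difference only. Any formal claim of similarity needs a margin justified in advance for that marker.

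The cost is a few lines of analysis text, with no extra participants or measurements. The drawback is that many null results, particularly at 30 per group with a half-width near 0.52 SD, will have to be reported as inconclusive.
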